1.1.9. Activity monitoring: At the end of the baseline assessment visit, eligible participants will be fitted with a commercially available physical activity monitoring device (ActiGraph Link), worn on the wrist. ActiGraph Link provides information about movement, rotation, and body position, that is used to determine intensity and amount of physical activity. Activity monitoring will be completed one-week prior to and one-week after completion of the intervention.

1.1.10. Exercise training session: After completion of the initial assessment visit and the activity monitoring period, two study team members will schedule a time to transport a study stationary bike to the participant's home via a university-owned vehicle, set-up the bike in the participant's home, and monitor the participant's first home-based exercise session in-person. Participants will also be provided with a study-owned tablet loaded with the application (described below) that will be used to administer and monitor their exercise regimen throughout the intervention.

1.1.11. Participants will complete one onsite exercise session, during which they will work with the exercise physiologist to determine the appropriate peddling speed corresponding to a moderate-intensity exercise zone based on the American College of Sports Medicine Guidelines. Heart rate and blood pressure will be monitored during this session to ensure that the participant does not exceed ACSM guidelines for safe activity.

1.1.12. Exercise intervention: The intervention will use personalized physical activity regimens that are remotely administered by exercise staff using an application called Neotiv. Neotiv has been programmed by a research group in Germany who have agreed to make it freely available for this pilot study. Neotiv is integrated with the stationary bike, allowing for the collection of data about speed, resistance, and duration of cycling. We will use Neotiv to monitor adherence to the intervention protocol and to adjust the protocol as needed. The participant will complete three exercise sessions per week on the bike at home for 12-weeks, which will gradually increase in duration from 15- to 50-minutes over the first month of the intervention. The final weekly exercise goal will be set to 150 minutes.

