Prior to initiating each exercise session, the participant will wear a Polar heart rate monitoring band around their chest, open the Neotiv application on the study tablet, at which time they will be prompted to rate their current mood using the Exercise

Induced Feeling Inventory (EFI)³⁰, which prompts respondents to rate the extent to which 12 different emotion words describe how they feel in the moment on a scale from 0 (“Do not feel”) to 4 (“Feel very strongly”). Example words include “Calm”, “Tired”, “Revived”, “Happy”, and “Fatigued”. The participant will then press the start button on the tablet application and begin exercise, at which time data from the exercise bike and the heart rate monitor will begin continuous transfer to the tablet in one-second intervals, via Bluetooth and ANT+ technology. Pleasant and relaxing images will be presented via the tablet during the exercise sessions to maintain interest and adherence. At the end of each exercise session, participants will be prompted to again rate their mood on the EFI and to rate their perceived exertion using the Borg scale from 6 to 20. After completion of the session the participant will press the end button on the tablet application and put the tablet in standby mode, unplug the stationary bike, and engage in 10-minutes of a stretching regimen taught by the exercise physiologist during the training session.

After completion of each exercise session, the following data will be sent to a subject-folder (named by study id) on a secure cloud-based platform (google firebase database set up for the study), which will be accessible to study staff: 1) heart rate per second 2) bike resistance per second, 3) peddling speed (rotations per minute), and 4) duration of exercise session. Study exercise staff will review these exercise data on a daily basis to monitor intervention adherence and will modify the exercise regimen (i.e., bike resistance) as required to ensure the participant is engaging in moderate-intensity exercise for the majority of each exercise session.

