1.2. Statistical Analysis Plan: This intervention is a pilot feasibility investigation. Therefore, the primary focus is on evaluating how successful we are at recruitment and retention, and whether we are able to keep participants engaged in the intervention. Although we will evaluate the effect of the intervention on cognitive and psychological functioning, is not intended to be statistically powered to address questions regarding the effectiveness of the intervention for improving the outcomes among adults exposed to early life adversity.

Aim 1a. The feasibility of this intervention will be assessed by examining average adherence rate over the course of the intervention, operationalized as a combination of number of sessions attended and average duration of each session. Average number of minutes spent in the 'moderate-intensity' heart-rate zone per session will also be examined. Threshold analysis will be conducted to understand whether exercise adherence declines after a certain time point in the intervention (e.g., 6-weeks). In an exploratory analysis, ActiGraph data will be used to assess whether engagement in the intervention results in an increase in physical activity from pre- to post-intervention.

Aim 1b. Intervention acceptability will be assessed through a self-report questionnaire completed post-intervention, including questions about satisfaction with various aspects of the intervention (i.e., intervention duration, interaction with study staff, use of technology to remotely guide intervention, overarching feedback about intervention, willingness to continue engaging in exercise).

Data related to 1) study enrollment and 2) summaries of weekly video/phone calls to monitor exercise adherence and engagement will be documented. The recruitment process (e.g., proportion of participants screened who enrolled in the study) and participants' experience in the intervention based on weekly phone sessions and the satisfaction questionnaire at the completion of the study will be qualitatively examined.

Aim 2. Paired sample T-tests will be used to assess change in cognitive and psychological functioning over the course of the 12-week intervention.

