- 1.3.4. Regarding exercise procedures, the most common injuries resulting from exercise are strained ligaments, muscles and joints along with delayed onset of muscle soreness. An exercise physiologist with a Master's degree in Exercise Science ([name]) and who has extensive experience monitoring exercise behaviors in normal and at risk populations will remotely monitor participants during all scheduled exercise sessions. Data to be monitored include heart rate (as collected via the Polar heart rate monitor), speed of pedaling, duration of exercise session, and ratings of perceived exertion. To avoid injuries, participants will gradually increase their exercise session duration and study intervention staff will be made fully aware of any pre-existing physical conditions that would require careful monitoring. All exercise sessions will be programmed to include a warmup and cool down period. Participants will also be reminded and encouraged to wear proper footwear and comfortable and appropriate workout attire for their exercise sessions. Potential problems such as dehydration, heat exhaustion and heat stroke are very uncommon and usually occur in athletes and others involved in extremely vigorous exercise. To prevent heat related illnesses, participants will be encouraged to regularly hydrate during exercise sessions, wear appropriate clothing, to open windows or turn on fans as needed, and to cease exercising if they feel they are becoming overheated. Prior to the start of the intervention, participants will be instructed about signs and symptoms of overexertion so that they can appropriately self-monitor during exercise sessions and stop exercising if needed.
- 1.3.5. With regards to exercise equipment malfunctions, these will be minimized by the fact that stationary bikes will only be used by one person for the duration of time that person is involved in the intervention. Staff will also be made available to complete repairs as needed and will query participants about any repair needs during weekly check-in calls.
- 1.3.6. Occasionally someone may develop heart trouble during exercise. Occurrence of such an event is extremely rare (as described in potential risks section above).

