However, to reduce the risk of heart troubles during exercise, participants with a history of heart disease will be ineligible to participate in this study. The study will follow ACSM guidelines in regards to contraindications to perform exercise, including systolic blood pressure > 190 mm Hg, diastolic blood pressure > 100 mm Hg, or heart rate > 100 beats per minute. These parameters will be evaluated during the exercise training session prior to the start of the intervention and participants will be disqualified if they exceed these recommendations. Once the intervention has begun, heart rate will be routinely monitored by exercise staff. If heart rate is observed to be abnormally high during home-based exercise sessions, exercise staff will contact the participants to discuss concerns and modify the exercise protocol as appropriate. If excess heart rate continues after modifications, exercise may be discontinued until the participant has been evaluated by a physician and has provided documentation of medical clearance to continue.

- 1.3.7. Exercise staff have completed a degree in Exercise Science or related field (e.g., kinesiology) and / or have a fitness certification from a reputable organization. All staff will have a minimum of 2 years of experience in exercise supervision and prescription. The exercise prescription level is moderate in intensity and the risk of a cardiac event occurring during exercise is 1 in 400,000 – 800,000 hours of exercise. Given this low level risk, it is not feasible to have a physician on site at each exercise session. All staff involved in the exercise intervention will review the emergency protocol of the hosting community centers. In addition, each session is staffed by individuals who are trained and certified in First-Aid, CPR, and AED use and oxygen administration. Both centers have first-aid kits, AED's and oxygen available at all times. Subjects will start with 10 - 15 minutes of moderate exercise and gradually increase as they can tolerate more. Level of increase will be individually based. This gradual increase is done to prevent injury. If subject becomes injured, they will need clearance from their physician in order to return to the intervention.

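### Mean minutes in the moderate heart-rate zone cannot show how often sessions met the protocol's own intensity aim, and it moves with session length and retention

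*Combined protocol and SAP*

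**What the plan says.** Section 1.2, Aim 1a, measures feasibility mainly by adherence, "operationalized as a combination of number of sessions attended and average duration of each session". That has no intensity component. Intensity enters through one further sentence: "Average number of minutes spent in the 'moderate-intensity' heart-rate zone per session will also be examined". The plan gives no denominator, no per-session criterion and no summary of time outside the zone.

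Section 1.1.12 describes delivery. On the schedule: "The participant will complete three exercise sessions per week on the bike at home for 12-weeks"; sessions "gradually increase in duration from 15- to 50-minutes over the first month of the intervention"; and "The final weekly exercise goal will be set to 150 minutes". On intensity, staff review the data daily and change bike resistance "to ensure the participant is engaging in moderate-intensity exercise for the majority of each exercise session". Heart rate per second and session duration are stored after every session.

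Section 1.1.11 links the zone to published exercise guidelines and does not give its heart-rate limits. Section 1.3.4 adds: "All exercise sessions will be programmed to include a warmup and cool down period". It does not give the length of either period. Section 1.3.6 sets out a staff response that begins: "If heart rate is observed to be abnormally high during home-based exercise sessions".

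**The concern.** The aim in 1.1.12 is a proportion that applies to each session. The planned summary is an absolute number of minutes, averaged over sessions whose scheduled length more than triples in the first month. The two can disagree in direction, and the summary changes with how long a participant stays in the study even if the way they exercise does not.

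No other planned analysis fills the gap. Borg ratings are collected after each session but do not appear in section 1.2. The ActiGraph is worn only in the week before and the week after the intervention.

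At stake is whether this pilot can tell the team planning the larger trial that remote delivery achieves the intended intensity. A low mean could reflect short sessions, early stopping, pedalling too lightly or working above the zone, and the planned figure does not distinguish these.

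**Working it through.** **Inputs (section 1.1.12).** Three sessions a week for 12 weeks; 15 minutes rising to 50 over the first month; weekly goal 150 minutes; aim of a majority of each session at moderate intensity, read as more than 50%.

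**The plan's own figure.** 3 × 50 = 150 minutes per week, which matches. Total sessions: 3 × 12 = 36.

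**1. The cut-off in minutes moves.** More than half of 15 is above 7.5 minutes; more than half of 50 is above 25. No single number of minutes represents the aim.

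**2. Order can reverse.** 9/15 = 60%, met; 20/50 = 40%, not met. Yet 9 < 20, so the session that met the aim scores lower.

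**3. Length and retention enter the mean.** The documents do not give the shape of the ramp. Assume equal weekly steps of 15, 26.7, 38.3 and 50 minutes, then 50 in weeks 5 to 12, an average over attended sessions only, full attendance until stopping, and 60% of every session in zone.
- Stops after week 4: mean duration (15 + 26.7 + 38.3 + 50)/4 = 32.5; minutes in zone 0.6 × 32.5 = 19.5.
- Completer: mean duration (12 × 32.5 + 24 × 50)/36 = 44.17; minutes in zone 0.6 × 44.17 = 26.5.

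Both met the aim in every session, and the measure differs by 7.0 minutes. The range over ramp shapes is:

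| Ramp in weeks 1–4 | Stops after week 4 | Completer | Gap |
|---|---|---|---|
| 15, 50, 50, 50 | 0.6 × 41.25 = 24.75 | 0.6 × 47.08 = 28.25 | 3.5 |
| 15, 26.7, 38.3, 50 | 19.5 | 26.5 | 7.0 |
| 15, 15, 15, 50 | 0.6 × 23.75 = 14.25 | 0.6 × 41.25 = 24.75 | 10.5 |

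**4. The same mean can hide different attainment.** This needs no ramp. In 50-minute sessions, 30 minutes in zone every time (60%) has mean 30 and meets the aim in 100% of sessions. Alternating 45 minutes (90%) and 15 minutes (30%) has mean (45 + 15)/2 = 30 and meets it in 50%.

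**5. Time outside the zone.** In a 50-minute session with 20 in zone, the other 30 may lie wholly below or wholly above it. The value is 20 either way. This assumes that the zone has an upper limit, which is the natural reading of a moderate zone but is not stated.

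**The case against.** The strongest reply is that 1.1.12 gives an instruction to staff, not a success criterion. The protocol's numerical goal is itself in minutes, so minutes in zone is a natural dose measure. After the first month sessions are scheduled at 50 minutes, where minutes and share rank single sessions identically. Average duration is also analysed, so an overall share can be derived. Much of this stands, and it is why mean minutes should be kept. It does not answer step 4: neither a mean nor a ratio of means shows how many sessions met the aim, even at constant length.

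Four stronger readings are tempting and are not supported.
- **Pooling.** A reader might infer that sessions are pooled across participants, so that frequent attenders dominate. Section 1.2 does not say so; averaging within participant first is an equally natural reading. The weighting is unstated.
- **Warm-up and cool-down.** A reader might infer that these bias the measure downwards. An absolute-minutes measure has no denominator for them to distort, and a majority aim leaves room for them.
- **Safety.** A reader might infer that failing to separate time above the zone is a safety defect. Section 1.3.6 concerns abnormally high heart rate, which is not the same as time above a moderate zone, and handles it through staff action. The 1.1.12 aim gives no credit for time above moderate either. What is lost is information.
- **Misleading success.** A reader might infer that the measure could make the trial look successful when it was not. No benchmark, test or progression rule is attached to it.

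**Conclusion.** The point holds as a mismatch between the delivery aim and the only planned intensity summary. That mean minutes cannot show per-session attainment, and that it can rank sessions the wrong way round, follows from the stated 15- and 50-minute lengths and needs no assumption beyond reading majority as more than half. The size of the mixing with retention is illustrative: 7.0 minutes under equal weekly steps and 3.5 to 10.5 minutes across the ramps shown, all at an assumed constant 60% in zone. The loss of the below/above distinction is a secondary point and rests on the zone having an upper limit. Priority is modest. The measure is descriptive, in a pilot that section 1.2 says is chiefly about recruitment, retention and engagement.

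**What to change.** In section 1.2, Aim 1a:
- Record the heart-rate limits of the zone. The planned minutes-in-zone measure already needs them, so this adds no new decision.
- For each session, compute the share of the whole session spent in zone from the stored per-second heart rate and session duration.
- For each participant, report the proportion of sessions with more than 50% of session time in zone, then summarise across participants. This also settles the weighting.
- Report time below, in and above the zone.
- Keep mean minutes in zone as a description of dose.
- If a version without warm-up and cool-down is wanted, label it a sensitivity version. It is a different criterion from the 1.1.12 aim: if the two periods took 10 of 50 minutes (an assumption, since no length is stated), the cut-off would fall from above 25 to above 20 minutes. It would also need these periods to be identifiable, and the list of stored data in 1.1.12 does not include markers for them.

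The cost is a few lines of SAP text and a little programming on data already stored. No visit, device or exercise rule changes.

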programmed to connect users with a trainer via an app. We will recruit individuals between the ages of 30-55 years ($N = 20$) from a well-characterized cohort of adults in Jamaica with early-childhood exposure to malnutrition and other forms of ELA (e.g., poverty) confirmed by contemporaneous medical records who continue to participate in research led by Co-Investigators and Reversibility Network members [name] and [name]. A comparison sample ($N = 20$) of age, sex, and race matched adults with an ELA history will be recruited in Pittsburgh, and a harmonized battery of cognitive, fitness, and psychosocial measures will be collected in both samples at baseline and following the 12-week intervention.

We have assembled a highly creative, productive, and interdisciplinary team with extensive experience conducting exercise interventions and evaluating indicators of brain health in multiple vulnerable populations (e.g., older adults with cognitive impairment, adults with a history of malnutrition). We will test the following aims:

Aim 1: Determine the feasibility and acceptability of a remote PA intervention among adults exposed to threat-related ELA living in Pittsburgh and Jamaica. It is hypothesized that the remote format of the intervention will enhance the feasibility of conducting a PA trial among individuals with a history of threat-related ELA.

Aim 2: Determine whether the remote PA intervention promotes improvements in cognitive and psychological functioning. It is hypothesized that cognitive and psychological functioning will improve over the course of the intervention and improvements will be greatest among those with the highest adherence rates.

The proposed research addresses the central goal of the NIA Reversibility Network to develop and test feasible interventions that may mitigate ELA-related risk for adverse health outcomes in adulthood. This pilot feasibility trial will set the groundwork for a larger-scale future R01 application that will test the efficacy of a remote PA intervention for improving brain health among adults who have been exposed to ELA. Further, the proposed research will provide an initial test of the impact of country-level factors (e.g., poverty rates, prevalence of more severe ELA such as malnutrition) on ELA-related disease burden in adulthood, information which may be leveraged to tailor interventions to meet the specific needs of the target population.

1.1 Overview of Methods:

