1.1.1. Subject recruitment, Pittsburgh: We expect to advertise through numerous outlets in order to enhance our ability to successfully recruit for the study. Participants ($N=20$) will be recruited via methods found to be effective in other studies, including the University of Pittsburgh online research registry (Pitt+Me) and community presentations at local community centers. We will also advertise on the Brain Aging and Cognitive Health (BACH) lab website (<http://bachlab.pitt.edu/>), lab social media accounts (Facebook & Instagram), and will post flyers and other ads around the Pittsburgh community.

1.1.2. Subject recruitment, Jamaica: Participants ($N=20$) will be recruited from across Jamaica, particularly from the areas within and surrounding Kingston, Jamaica where the University of the West Indies is located. Participants will be age, sex, and race matched across sites.

1.1.3. Eligibility criteria: Inclusion criteria will be as follows: 1) adults aged 30-55 years, 2) exposure to at least one form of threat-related ELA (e.g., exposure to violence; physical abuse) prior to the age of 10 as documented by retrospective self-report (described in detail below), 3) self-identified Black or African American race, 4) access to high-speed internet, and 5) sedentary lifestyle (<60 minutes of PA/week). Exclusion criteria will include: 1) psychosis, 2) significant suicide risk (i.e., current, active suicidal ideation with a plan), 3) engaging in moderate-intensity exercise >=20 min per day, >=3 times per week, 4) current treatment for cancer, 5) neurological condition (e.g., MS, Parkinson's, Dementia, MCI) or brain injury (e.g., stroke), 6) substance use disorder in the past 3-months, 7) current treatment for congestive heart failure, angina, uncontrolled arrhythmia, DVT or other cardiovascular event, 8) myocardial infarction, coronary artery bypass grafting, angioplasty or other cardiac condition in the past year, 9) sensory impairment that would preclude neuropsychological testing, 10) not fluent in English, 11) travelling consecutively for 2+ weeks during the study, 12) uncontrolled hypertension, 13) insulin-dependent Diabetes Mellitus, and 14) self-identified as any race other than Black or African American.

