Aim 3: Attendance and adherence rates, as well as participant satisfaction ratings, will be compared using Paired sample T-tests to determine whether there are differences in these metrics across sites. Statistical tests performed to assess Aim 2 will be repeated separately for each site to evaluate whether effect sizes differ by site.

1.3. Minimization of Risks:

1.3.1. To reduce the risk for breach of confidentiality we will separate all information obtained during the screening period from identifying documents. All research data will be de-identified. These documents will be stored in a separate location from the data and the screening information in locked filing cabinets in a locked and secure room that only lab personnel have access to. Data that is saved electronically (computer system) is protected by the University of Pittsburgh firewalls. Regarding heart rate data collected via the Polar app, these data will only

be stored on the app temporarily (i.e., during the exercise session) in order to continuously monitor safety. This information will be transferred to our secure server as soon as possible after each session to minimize risk of breached confidentiality.

- 1.3.2. Subject privacy will be maintained in this research study by having all participants answer questions and perform cognitive tasks in an isolated and private room. All of the information that we will collect in this protocol is essential for the research questions we are posing. In this way, there will be no unnecessary personal information collected from these participants.

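### Aim 3 asks whether effects differ by site, but separate paired t-tests within each site neither estimate nor test that difference

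*Combined protocol and SAP*

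**What the plan says.** All of the relevant analysis text is in section 1.2 of the combined protocol and SAP.

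- **Aim 2** sets the test: "Paired sample T-tests will be used to assess change in cognitive and psychological functioning over the course of the 12-week intervention". It has no site term and mentions no interval.
- **Aim 3, first sentence**, plans a direct comparison between sites, but only for attendance, adherence and satisfaction. Its purpose is "to determine whether there are differences in these metrics across sites".
- **Aim 3, second sentence**, covers the cognitive and psychological outcomes: "Statistical tests performed to assess Aim 2 will be repeated separately for each site to evaluate whether effect sizes differ by site".
- **Opening paragraph** says of the study that it "is not intended to be statistically powered to address questions regarding the effectiveness of the intervention".

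On the sample, section 1.0 plans 20 adults in Pittsburgh as the comparison group, and section 1.1.2 plans 20 in Jamaica. Section 1.1.2 adds: "Participants will be age, sex, and race matched across sites". It does not say whether individuals are paired or the groups are balanced overall.

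**The concern.** The purpose stated in Aim 3 is a comparison of two changes. The method given is two separate tests, each comparing one site's change with zero. Neither result, nor the two together, is a test or an estimate of the difference. The sentence just before does plan a cross-site comparison for the adherence and satisfaction measures, so the Aim 2 outcomes are the ones left without a contrast.

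A reader would have to set two p-values or two effect sizes side by side, each from at most 20 people. Read as significant versus not significant, they can suggest a site difference where the true changes are equal. Read descriptively, nothing shows how much of the gap is chance. Either way, a chance gap could be carried into the design of the larger trial that section 1.0 says this pilot prepares for.

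**Working it through.** **Inputs.** From the documents: 20 participants per site (sections 1.0 and 1.1.2) and pre-post paired t-tests repeated by site (section 1.2). The documents give no alpha, sidedness, SD, effect size or dropout, and no power figure to reproduce. Assumed: two-sided alpha 0.05, independent sites, equal SD of change, and changes in SD-of-change units. A second case assumes 20% dropout, so 20 × 0.8 = 16 completers per site.

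**1. Descriptive reading, equal true changes.** The standard error of the gap between two site means is √(2/n), which is 0.316 for n = 20 and 0.354 for n = 16. The chance of a gap of at least g is 2 × [1 − Φ(g/SE)].

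| Gap | n = 20 | n = 16 |
|---|---|---|
| ≥ 0.3 SD | 0.3/0.316 = 0.949 → 34% | 0.3/0.354 = 0.849 → 40% |
| ≥ 0.5 SD | 0.5/0.316 = 1.581 → 11% | 0.5/0.354 = 1.414 → 16% |

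These treat the SD as known and common. If each change is divided by its own site's SD, simulation at a true change of 0.4 SD with n = 20 gives about 38% and 15%, so the table slightly understates the scatter.

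**2. Significant-versus-not reading, equal true changes.** Let p be the power of one within-site test (noncentral t, n − 1 df, noncentrality change × √n). The chance that exactly one site is significant is 2p(1 − p).

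| Common true change (SD) | p, n = 20 | Exactly one significant, n = 20 | Exactly one significant, n = 16 |
|---|---|---|---|
| 0 | 0.050 | 9.5% | 9.5% |
| 0.2 | 0.136 | 23.5% | 21% |
| 0.3 | 0.247 | 37% | 32% |
| 0.4 | 0.397 | 48% | 44% |
| 0.5 | 0.565 | 49% | 50% |
| 0.6 | 0.721 | 40% | 47% |
| 0.8 | 0.924 | 14% | 26% |
| 1.0 | 0.989 | 2% | 7% |

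A direct test of the difference rejects in 5% throughout. All rates are per outcome. Section 1.1.8.1.1 lists six NIH Toolbox tasks and section 1.1.7.1 lists five psychological questionnaires.

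**3. An example, n = 20.** Observed changes of 0.50 and 0.40 SD give t = 0.50 × √20 = 2.24 (p = 0.038) and t = 0.40 × √20 = 1.79 (p = 0.090). One site is significant and the other is not. The direct contrast is 0.10 SD, with 95% CI 0.10 ± 0.64, or −0.54 to 0.74, and p = 0.75.

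**4. What a direct contrast delivers.** The 95% half-width is t(0.975, 2n − 2) × √(2/n).

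- n = 20: 2.024 × 0.316 = 0.64 SD. Power is about 15% for a true site difference of 0.3 SD, 34% for 0.5 and 69% for 0.8. It reaches 80% at about 0.91 SD.
- n = 16: 2.042 × 0.354 = 0.72 SD, with 80% power at about 1.02 SD.
- If individuals are paired across sites (n = 20), the half-width is 2.093 × √(2(1 − ρ)/20): 0.66, 0.59 or 0.47 SD for an assumed within-pair correlation ρ of 0, 0.2 or 0.5.

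**The case against.** The strongest reply is that the plan speaks of effect sizes and never says a site difference will be declared when one p-value falls below 0.05 and the other does not. The 24–49% rates at 0.2–0.6 SD belong to a rule the plan does not state. This is fair, and the descriptive figures should carry more weight; those are ordinary sampling scatter, not an error rate. But the plan does repeat statistical tests, so p-values would be on the page, and under the descriptive reading there is still no measure of uncertainty for the gap.

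Second, this is a pilot. Section 1.2 puts the focus on recruitment, retention and engagement, and section 1.0 lists only Aims 1 and 2. That limits the weight of the point. It does not withdraw the question Aim 3 asks, and small samples make an interval more useful.

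Third, the direct contrast has little power, so real site differences would often be missed with it too. This stands: the gain is an honest statement of uncertainty, not better detection.

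Fourth, if the sites are independent, a reader given each site's mean change, SD and n could work out the contrast, and the short SAP gives no intervals for any analysis. This softens the point, but the plan does not commit to reporting those summaries.

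**Conclusion.** The concern holds, with high confidence. The method named in Aim 3 does not answer the question in the same sentence, and nothing elsewhere in the document supplies a between-site contrast for the Aim 2 outcomes. That conclusion follows from the wording and needs no assumed figure.

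The size of the problem does rest on the assumptions listed above. Under them, sizeable chance gaps between sites are common even when the true changes are equal, and a significant-versus-not reading would suggest a difference far more often than the 5% of a direct test for common changes of about 0.2 to 0.6 SD. The change should be made, but feasibility conclusions are untouched.

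**What to change.** Add to Aim 3 in section 1.2 wording such as:

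> For each Aim 2 outcome, the between-site difference in mean pre-post change will be reported with its 95% CI (two-sample comparison of change scores, equivalently the site-by-time term) and labelled exploratory. If individuals are matched in pairs across sites, the analysis will respect the pairing. Site-specific mean changes with 95% CIs are descriptive; site differences will be judged only from the contrast. A non-significant contrast will not be taken to show that the sites are alike.

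The SAP should also say whether matching is individual or by group, since that decides which form applies. A baseline-adjusted model is at most an optional sensitivity analysis: sites are not randomised, and it estimates a different quantity. For the same reason, any site difference is confounded with country and recruitment source and should be described that way.

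The cost is a few sentences and one extra estimate per outcome from data already collected. The drawback is a wide interval, which the report should show plainly.
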